6.8. Treatment After the End of the Study

Upon completion of the 36 weeks of treatment, participants will not be provided additional treatment within this study.

7. DISCONTINUATION OF STUDY TREATMENT AND PARTICIPANT WITHDRAWAL

7.1. Discontinuation of Study Treatment

7.1.1. Reasons for Discontinuation

Participants **must** be discontinued from study treatment for the following reasons:

- The participant becomes pregnant.
- Consent is withdrawn.

Note: Consent withdrawn means that the participant has explicitly indicated that they do not want to be followed any longer; in this case no further data, except data in the public domain, may be solicited from or collected on the participant. Consent may also be partial. Participants may choose to discontinue study drug and remain in the study to complete the post-treatment follow-up visit.

- Further participation would be injurious to the participant's health or well-being, in the investigator's medical judgment.
- Occurrence of unacceptable toxicity as noted in Section 6.6.
- Has received a prohibited medication or procedure as described in Section 6.7.4.
- The study is terminated by the sponsor.
- The study is terminated by the local health authority, IRB, or IEC.

A participant **may** be discontinued from study treatment as follows:

- If a participant is consistently noncompliant with study procedures or with study drug or background therapy administration in the investigator's opinion, the sponsor should be consulted for instruction on handling the participant.

7.1.2. Discontinuation Procedures

In the event that the decision is made to permanently discontinue the study treatment, the EOT/ET visit should be conducted (see Section 8.7). Reasonable efforts should be made to have the participant return for a post-treatment follow-up visit. These visits are described in Table 3. The last date of the last dose of study drug and the reason for discontinuation of study drug will be recorded in the eCRF.

If a participant is discontinued from study treatment:

- The study monitor or sponsor must be notified.
- The reason(s) for discontinuation must be documented in the participant's medical record and the primary reason for discontinuation must be included in the eCRF.
- The EOT/ET visit should be performed and date recorded.

- The status of the participant should be updated to EOT in the IRT.
- Participants must be followed for safety until the time of the post-treatment follow-up visit or until study drug-related toxicities resolve, return to baseline, or are deemed irreversible, whichever is longest.

If the participant discontinues study treatment and actively withdraws consent for collection of follow-up data (post-treatment follow-up or disease assessment), then no additional data collection should occur; however, participants will have the option of withdrawing consent for study treatment but continuing in the follow-up period of the study for safety/efficacy assessments.

7.2. Participant Withdrawal From the Study

A participant may withdraw from the study at any time at their own request or may be withdrawn at any time at the discretion of the investigator for safety, behavioral, compliance, or administrative reasons.

If a participant withdraws from the study, they may request destruction of any samples taken and not tested, and the investigator must document this in the site study records. If the participant withdraws consent for disclosure of future information, the sponsor may retain and continue to use any data collected before such a withdrawal of consent.

See [Table 3](#) for data to be collected at the time of study withdrawal and follow-up and for any further evaluations that need to be completed.

7.3. Lost to Follow-Up

A participant will be considered lost to follow-up if they repeatedly fail to return for scheduled visits and are unable to be contacted by the study site.

The following actions must be taken if a participant fails to return to the clinic for a required study visit:

- The site must attempt to contact the participant and reschedule the missed visit as soon as possible and counsel the participant on the importance of maintaining the assigned visit schedule and ascertain whether or not the participant wishes to and/or should continue in the study.
- Before a participant is deemed lost to follow-up, the investigator or designee must make every effort to regain contact with the participant (where possible, 3 telephone calls and, if necessary, a certified letter to the participant's last known mailing address or local equivalent methods). These contact attempts should be documented in the participant's medical record.
- Should the participant continue to be unreachable, they will be considered to have withdrawn from the study.

8. STUDY ASSESSMENTS AND PROCEDURES

See [Appendix E](#) for COVID-19–related guidance.

8.1. Administrative and General Procedures

8.1.1. Informed Consent Process

- The investigator or their representative will explain the nature of the study to the participant and answer all questions regarding the study.
 - Informed consent must be obtained before any study-related procedures are conducted, unless otherwise specified by the Protocol.
 - Informed consent must be obtained using the IRB/IEC-approved version in a language that is native and understandable to the participant. An ICF template will be provided by the sponsor or its designee. The sponsor or its designee must review and acknowledge the site-specific changes to the ICF template. The ICF must include a statement that the sponsor or its designee and regulatory authorities have direct access to participant records.
 - The ICF must contain all required elements including optional samples/procedures (eg, optional biopsy) and describe the nature, scope, and possible consequences of the study in a form understandable to the study participant.
- Participants must be informed that their participation is voluntary. Participants will be required to sign a statement of informed consent that meets the applicable requirements and regulations for the countries in which the study is being conducted as well as the IRB/IEC or study center.
- The participant must be informed that their personal data collected for the study will be used by the sponsor and/or their designee(s) in accordance with local data protection laws. The level of disclosure must also be explained to the participant.
- The participant must be informed that their medical records may be examined by Clinical Quality Assurance auditors or other authorized personnel appointed by the sponsor, by appropriate IRB/IEC members, and by inspectors from regulatory authorities.
- The medical record must include a statement that written informed consent was obtained before the participant was enrolled in the study and the date the written consent was obtained. The authorized person obtaining the informed consent must also sign the ICF.
- Participants must provide consent to the most current version of the ICF during their participation in the study.
- A copy of the ICF(s) must be provided to the participant or the participant's legally authorized representative.

Participants who are rescreened are required to sign a new ICF and be assigned a new participant number (see Section [8.1.3](#)).

8.1.2. Screening Procedures

Screening is the interval between signing the ICF and the day the participant is randomized in the study (Day 1/baseline). Screening may not exceed 28 days. Assessments that are required to demonstrate eligibility may be performed over the course of 1 or more days during the screening process. A signed ICF must be obtained as the first step and before IRT screening registration or any other study-specific assessments. The screening of a participant should be registered in the IRT, which will assign the study-specific ID. Each participant who has signed the ICF should be registered in the IRT contemporaneously and without undue delays.

Results from the screening visit evaluations will be reviewed to confirm eligibility before the randomization transaction is registered in the IRT and before the administration of study drug. Tests with results that fail eligibility requirements may be repeated once during screening if the investigator believes the results to be in error. For screening assessments that are repeated, the most recent available result before randomization will be used to determine eligibility.

See Sections 5.4 and 5.5 for information regarding screen failures and replacement of participants, respectively.

8.1.3. Interactive Response Technology Procedure

Each participant will be identified in the study by a participant ID number, which is a combination of the country's abbreviation, the site ID, and the participant number. Site staff should contact the IRT to obtain the participant ID number during screening.

Upon determining that the participant is eligible for randomization, the IRT will be contacted to obtain the treatment assignment. Additionally, the IRT will be contacted at the study visits indicated in Table 3 to update the study drug supply. Additional details will be provided in the IRT manual.

8.1.4. Distribution of Reminder Cards

Participants will be provided with a reminder card at each visit indicated in Table 3.

The reminder card will provide general information regarding study drug administration, including on which study visit days the participant should not self-administer their dose of study drug.

8.1.5. Distribution of Participant Cards

Participants will be provided with a participant card at screening.

Participants should be instructed to carry this card at all times and to present it to all healthcare professionals when either visiting any other medical facility or department other than the study site or hospitalized. The participant card will contain the name and contact details for the investigator.

8.1.6. Distribution of Electronic Diaries

Participants will be provided with an eDiary at screening.

Sites will be provided with training materials and instructions on the use of eCOA and will be responsible for training participants on eDiary use and eCOA completion. Further details on use

of the eDiaries and eCOA will be provided in respective study documentation. For PROs scheduled to be completed at study visits, questionnaires will be completed by the participant before site personnel perform any clinic assessments to avoid biasing the participant's response.

8.1.7. Demography and Medical History

8.1.7.1. Demographics and General Medical History

Demographic data and general medical history will be collected at screening by the investigator or qualified designee and will include year of birth/age, race, ethnicity, medical and surgical history, family history of cardiovascular disease, family history of clotting disorders, risk factors associated with cardiovascular disease, history of nicotine and alcohol use, and current illnesses. Medical history will include relevant medical and surgical treatments that are considered to be clinically significant by the investigator.

History of clinical herpes zoster, herpes zoster vaccination, chickenpox vaccination, influenza vaccination, and hepatitis B vaccination status will be recorded as part of the medical history.

History of COVID-19 vaccination and COVID-19 infection (and/or hospitalization) will be recorded as part of the medical history.

A detailed medical history with respect to TB risk factors will be documented in the study source documentation. This information will include BCG vaccination; cohabitation with individuals who have had TB; and travel to, residence in, or work in TB endemic locations.

8.1.7.1.1. Justification for Collection of Race and Ethnicity

Epidemiologic estimates for CSU are sparse, and the impact of race and ethnicity on CSU is not yet understood. Demographic data, including race and ethnicity, will be collected during the screening period for this study and considered as part of assessments for treatment response heterogeneity.

8.1.7.2. Disease Characteristics and Treatment History

Complete CSU medical and treatment history, including date of diagnosis, relevant disease characteristics, and prior treatments, including systemic treatments, will be collected at screening. A medical history of other conditions related to CSU or relevant to the conduct of this study will also be collected at screening.

Additional information on the procedure for collection of prior CSU therapy and ongoing background therapy information is presented in Sections 6.7.1 and 6.7.2, respectively.

8.2. Efficacy Assessments

Efficacy will be evaluated using PRO measures in this study.

8.2.1. Patient-Reported Outcomes

All PROs will be collected via eCOA.

8.2.1.1. Daily Diary Patient-Reported Outcomes

8.2.1.2. Administrative Procedures

8.2.1.2.1. Follow-Up Phone Call

Study sites should contact participants 1 week prior to the baseline visit, 2 weeks prior to the Week 4 visit, and 1 week prior to the Week 12 visit to confirm compliance with the daily diary assessments.

8.2.1.2.2. Compliance With Daily Diary Patient-Reported Outcomes

Participants' compliance with daily diary PRO assessments (ie, ISS, HSS [REDACTED]) should be monitored by the investigator (or designee) throughout the study. Compliance will be evaluated as outlined below:

- Screening period:
 - A minimum of 5 daily diary assessments should be completed within the 7 days before the baseline visit.
- PC and EXT periods:
 - Participants' compliance with the daily diary assessments should be assessed at each study visit during the PC and EXT periods.
 - Participants who are consistently noncompliant with the daily diary assessments may be withdrawn from the study.

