Contact IRT	X	X	X	X	X	X	X	X	X	X	X			Section 8.1.3
Dispense eDiary (handheld device) and instruct participant on use	X													Section 8.2.1.3
Randomization		X												Section 6.4
Dispense study drug		X	X	X	X	X	X	X	X	X				Section 6.1
Administer study drug at site		X	X	X	X	X	X	X	X	X	X			
Administer background therapy at site		X	X	X	X	X	X	X	X	X	X			
Distribute reminder card	X	X	X	X	X	X	X	X	X	X	X			Section 8.1.4
Distribute participation card	X													Section 8.1.5

Table 3: Schedule of Activities (Continued)

Visit Day (Range)	Screening	PC Period (12 Weeks)				EXT Period (24 Weeks)						Post-Treatment Follow-Up	Notes and Protocol Section
	Days -28 to -1	Baseline Day 1	Week 4 (± 3 d)	Week 8 (± 3 d)	Week 12/ EOT1 (or ET1) (± 3 d)	Week 16 (± 3 d)	Week 20 (± 3 d)	Week 24 (± 3 d)	Week 28 (± 3 d)	Week 32 (± 3 d)	Week 36/ EOT2 (or ET2) (± 3 d)	Week 44/ EOS (± 7 d)	
Administrative procedures (continued)													
Collect study drug and review drug compliance			X	X	X	X	X	X	X	X	X		Section 6.5
Follow-up phone call for eDiary compliance	X*		X†		X*								Section 8.2.1.2.1 * 1 week before visit. † 2 weeks before visit.
Review eDiary compliance		X	X	X	X	X	X	X	X	X	X		Section 8.2.1.2.2
Safety assessments													
AE assessments	X	X	X	X	X	X	X	X	X	X	X	X	Section 8.3.1
Contraception check	X	X	X	X	X	X	X	X	X	X	X	X	Section 5.3.1
Comprehensive physical examination	X				X						X		Section 8.3.2
Targeted physical examination		X	X	X		X	X	X	X	X		X	
Weight/height	X	X			X			X			X	X	Section 8.3.2 Height at screening only.
Vital signs	X	X	X	X	X	X	X	X	X	X	X	X	Section 8.3.3
12-lead ECG	X				X						X		Section 8.3.4

Table 3: Schedule of Activities (Continued)

Visit Day (Range)	Screening	PC Period (12 Weeks)				EXT Period (24 Weeks)						Post-Treatment Follow-Up	Notes and Protocol Section
	Days -28 to -1	Baseline Day 1	Week 4 (± 3 d)	Week 8 (± 3 d)	Week 12/ EOT1 (or ET1) (± 3 d)	Week 16 (± 3 d)	Week 20 (± 3 d)	Week 24 (± 3 d)	Week 28 (± 3 d)	Week 32 (± 3 d)	Week 36/ EOT2 (or ET2) (± 3 d)	Week 44/ EOS (± 7 d)	
Efficacy assessments													
PROs													
eDiary (UAS/AAS)	Daily from screening through Week 44 (or ET, if applicable)											Sections 8.2.1.3, 8.2.1.4, and 8.2.1.5 Handheld device.	
Quality of life assessments													
Laboratory assessments													
Serum FSH (WONCBP only)	X												Section 8.3.5

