6.5.1. Compliance With Povorcitinib/Placebo

Compliance with study drug will be calculated by the sponsor based on the drug accountability (eg, tablet counts) documented by the site staff and monitored by the sponsor/designee. Participants will be instructed to bring all unused study drugs with them to the study visits in order for site personnel to conduct tablet counts to assess study drug accountability.

Compliance with study drug will be calculated for the PC and EXT periods based on the following:

Within the PC period:

- The first dose will occur on Day 1 (baseline).
- The last dose will occur on the day of the Week 12 visit or the day of the last study drug administration known to the investigator (or designee) as reported in the EDC for participants who prematurely discontinue study treatment or are lost to follow-up.

Within the EXT period:

- The first dose will occur the day after the Week 12 visit.
- The last dose will occur on the day of the Week 36 visit or the day of the last study drug administration known to the investigator (or designee) as reported in the EDC for participants who prematurely discontinue study treatment or are lost to follow-up.

Participants' compliance must be within 80% to 120% assessed at each study visit by the investigator (or designee). If outside of this range, it will be considered a Protocol deviation. Participants consistently noncompliant with the study drug may be withdrawn from the study. The decision on withdrawal will be made by the investigator after consultation with the sponsor, and relevant correspondence will be archived in the site study file.

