8.2.1.4.1. Urticaria Activity Score Over 7 Days

The UAS7 is the 7-day sum of the daily UAS. The UAS7 (range 0 to 42) is equal to the ISS7 (range 0 to 21) plus the HSS7 (range 0 to 21).

If a participant has entered at least 5 daily UAS scores within the 7 days prior to the study visit, the UAS7 score is calculated as the sum of the available UAS scores, divided by the number of days that have a UAS score, multiplied by 7.

If there are more than 2 daily UAS scores missing within the prior 7 days, then the UAS7 score is missing for the week.

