10.4.1. Primary Analysis

The primary estimand and the strategies for addressing the defined intercurrent events are provided in [Table 15](#) and [Table 16](#), respectively.

Table 15: Estimand for Primary Endpoint

Primary Endpoint	Population	Treatment	Population-Level Summary
Change from baseline in the weekly UAS7 at Week 12.	Participants aged 18 to 65 years who have had a diagnosis of CSU for ≥ 3 months that is inadequately controlled by second-generation H1 antihistamines.	Each of the povorcitinib dose groups compared with placebo	The estimated mean change from baseline in UAS7 for each treatment group, as well as the difference in the estimated mean change from baseline in UAS7 score in each active treatment group as compared with the placebo group, at Week 12.

Table 16: Intercurrent Events and Strategies for the Primary Estimand

Intercurrent Event	Strategies for Addressing the Intercurrent Event
Treatment discontinuation due to any reason	The data collected for the variable are used regardless of whether or not the participant discontinues treatment due to any reason (treatment policy strategy)
Initiation of Protocol-allowed rescue medication	The data collected for the variable are used regardless of whether or not the participant starts the use of any Protocol-allowed rescue medication (treatment policy strategy)

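### Withdrawing participants from the study for poor diary or drug compliance before Week 12 creates avoidable missing primary-endpoint data, and the protocol sections that allow it need reconciling

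*Protocol*

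**What the plan says.** Four protocol passages deal with noncompliance.

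- Section 8.2.1.2.2, on the diary in the PC and EXT periods: "Participants who are consistently noncompliant with the daily diary assessments may be withdrawn from the study".
- Section 6.5.1, on study drug: "Participants consistently noncompliant with the study drug may be withdrawn from the study". The investigator decides after consulting the sponsor.
- Section 7.2, on study withdrawal in general: a participant "may be withdrawn at any time at the discretion of the investigator for safety, behavioral, compliance, or administrative reasons".
- Section 7.1.1, on stopping study treatment, lists as a possible reason: "If a participant is consistently noncompliant with study procedures or with study drug or background therapy administration in the investigator's opinion". The sponsor is to be consulted on handling.

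For drug compliance the protocol gives a range of 80% to 120%. For the diary it sets no threshold after baseline, and neither section defines what counts as consistent noncompliance.

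The data needed at Week 12 are limited. Section 8.2.1.4.1 calculates the score as follows: "If a participant has entered at least 5 daily UAS scores within the 7 days prior to the study visit", the available scores are averaged and scaled to 7 days. Section 8.2.1.2.1 has the site call the participant about the diary 1 week before the Week 12 visit. The diary row of the Schedule of Activities (Protocol Table 3) reads "Daily from screening through Week 44 (or ET, if applicable".

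For treatment discontinuation, Protocol Table 16 says "The data collected for the variable are used regardless of whether or not the participant discontinues treatment due to any reason (treatment policy strategy". SAP Table 5 agrees. Neither table lists study withdrawal as an intercurrent event.

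**The concern.** The primary endpoint and all three secondary endpoints come from this diary. Compliance is reviewed at each visit, so a participant could be removed at Week 4 or Week 8, before the Week 12 diary week opens. Neither the reminder call nor the diary week would then take place, and a score that might have been missing becomes one that is certainly missing.

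The analyses feel this in three ways.

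- **Primary MMRM:** missing data are not imputed, and anyone without a postbaseline value is left out (Protocol Section 10.4.1, SAP Section 7.3).
- **Responder endpoints:** under SAP Section 7.4.1 a participant without a Week 12 response is a nonresponder, so a conduct decision can be counted as treatment failure.
- **Time to UAS7 of 6 or less:** follow-up is censored at the last available score.

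A treatment-policy estimand depends on data collected after people stop adhering. A rule that removes nonadherent people from the study works against it. The sample-size sections state no dropout allowance. Protocol Section 5.5 rules out replacement, apart from possible extra recruitment because of COVID-19.

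**Working it through.** **1. The plan's own power.** Inputs from Protocol Section 10.1 and SAP Section 3.3: doses 0, 15, 45 and 75 mg; 34 per group; largest effect 17 − 8 = 9; SD 13; 1-sided alpha 0.025; six candidate models. For each model the optimal contrast is c = (μ − mean μ), scaled to unit length. The test takes the largest of the six contrast t statistics. The multiplicity-adjusted critical value is 2.181 on 132 df (400,000 simulated draws).

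The linear model has the lowest power. Its means above placebo are 0, 1.8, 5.4 and 9, with average 4.05. The squared deviations are 16.40, 5.06, 1.82 and 24.50, sum 47.79, root 6.913. The noncentrality is √34 × 6.913 / 13 = 3.10. Taking the largest of the six statistics gives power 0.850, against 0.85 stated. The other rows also reproduce: 0.849 for 29 per group and SD 12 (stated 0.84), and 0.856 for 25 per group and SD 11 (stated 0.85).

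**2. Power if some participants contribute nothing.** The share w is assumed, because the documents give no rate. Put n = 34(1 − w) into the same calculation. The last column is 34/(1 − w), rounded up.

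| w | n per group | Minimum power | n per group to offset |
|---|---|---|---|
| 0 | 34 | 0.850 | 34 |
| 3% | 33.0 | 0.838 | 36 |
| 5% | 32.3 | 0.831 | 36 |
| 10% | 30.6 | 0.810 | 38 |
| 15% | 28.9 | 0.787 | 40 |
| 20% | 27.2 | 0.761 | 43 |

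For a given w these losses are upper bounds, because the MMRM still uses any Week 4 and Week 8 scores.

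**3. Who could still supply a Week 12 score.** Assume days are independent, with daily completion rate p. Then P(at least 5 of 7) = 21p⁵(1 − p)² + 7p⁶(1 − p) + p⁷. At p = 0.5 this is (21 + 7 + 1)/128 = 0.227.

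| p | 0.3 | 0.4 | 0.5 | 0.6 | 0.7 | 0.8 |
|---|---|---|---|---|---|---|
| P(at least 5 of 7) | 0.03 | 0.10 | 0.23 | 0.42 | 0.65 | 0.85 |

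Withdrawal before the diary week sets each of these to 0. Retention recovers only part of the loss. If 10% of an arm (3.4 people) were diary noncompliers completing 60% of days, keeping them would yield about 3.4 × 0.42 = 1.4 scores. People who are noncompliant with drug alone may keep a good diary, so their loss is the most avoidable.

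**4. Possible bias.** If withdrawn participants' true Week 12 change differed from what the model implies by 3 to 9 points (assumed), an arm mean would shift by w times that difference. This is 0.15 to 0.45 points at w = 5% and 0.3 to 0.9 points at w = 10%, against a planned effect of 9. On a responder endpoint, each withdrawn person who would have responded costs the arm 1/34 = 2.9 percentage points.

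**5. The two routes side by side.** Sections 6.5.1, 7.2 and 8.2.1.2.2 lead to leaving the study. Section 7.1.1 leads to stopping treatment. The second route does not clearly secure the data either. Section 8.7 calls for an ET visit when study drug is permanently stopped, and the diary row ends at ET where applicable. Section 7.1.2 lets a participant stay on for follow-up assessments, but as the participant's option. No passage schedules a Week 12 diary week for someone who stops treatment in the PC period.

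**The case against.** The strongest reply is that these are ordinary discretionary clauses. Every one of them is permissive, and for drug noncompliance the sponsor must be consulted. Withdrawal in the EXT period cannot affect Week 12, and only the Week 4 and Week 8 reviews fall between baseline and the endpoint. This stands. A reader might infer that the rule guarantees missing data; it does so only when used before the Week 12 diary week.

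A reader might also infer that the rule contradicts the estimand. It does not. Treatment policy is specified for treatment discontinuation and allowed rescue, and it applies to data collected. Study withdrawal is a missing-data matter here.

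Nor is there a strict contradiction between sections. Section 7.2 expressly allows withdrawal for compliance reasons and Section 7.1.1 does not forbid it. These are overlapping permissions, but they leave a site free to choose between two actions with different consequences for the data.

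Many consistent diary noncompliers would miss 5 of 7 days anyway. The protocol's only numerical diary standard is 5 of 7 days (71%) at screening, so a person completing 80% of days would meet it. That such withdrawals would track perceived lack of benefit is plausible, but the documents do not show it.

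Earlier diary gaps do matter to the MMRM visits and to the time-to-event endpoint. Withdrawal repairs none of those gaps. Training, calls and visit reviews already exist, which makes retention cheap but does not remove the withdrawal rule.

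**Conclusion.** The point holds as an inexpensive improvement to the protocol. Used before the Week 12 diary week, compliance-based withdrawal can only lose primary-endpoint data, and the loss is avoidable and possibly related to outcome. It undermines the treatment-policy estimand and makes the participant a nonresponder on the two responder endpoints.

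The size is probably modest. Minimum power falls from 0.85 to about 0.83 to 0.81 at most, if 5% to 10% of each arm contribute nothing. That range is assumed, as are the independent diary days and the 3- to 9-point difference behind the bias figures. The stated power is not in error.

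**What to change.** 1. Reconcile Sections 6.5.1, 7.1.1, 7.2 and 8.2.1.2.2 on whether noncompliance leads to study withdrawal or to treatment discontinuation. This review takes no position on when study drug should stop.
2. State that diary or drug noncompliance alone is not a reason to withdraw a participant from the study before Week 12. Section 7.2 must carry this too, or its general compliance power would override the change.
3. For diary gaps in the PC period, replace the withdrawal sentence in Section 8.2.1.2.2 with retraining and reminder contact.
4. State in the diary row of the Schedule of Activities and in Section 7.1.2 that diary collection and the Week 12 assessment continue for every PC-period participant unless consent is withdrawn.

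The cost is protocol wording and some reminder effort at sites. Some Week 12 scores will still be missing.
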